**Secondary Aim 2:** One secondary aim of this project is to quantify the contraceptive continuation and satisfaction rates of the participants randomized to LNG-IUS. The objective of this aim is to demonstrate that if women have access to the LNG-IUS in this time period, most will continue use for at least 12 months and will have high levels of satisfaction. *Hypothesis:* Greater than 70% of women receiving the LNG-IUS as EC will have continued use and satisfaction.

It is our *expectation* that the information gained from completion of this aim will contribute to the growing body of literature describing continuation and satisfaction rates among different groups of LARC users.

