At the follow-up phone surveys, individual level information will be updated with new medical data including any new medical diagnosis, interval pregnancies since enrollment, and interval diagnosis of STIs. We will also assess fertility desires, recent and current contraceptive use, and recurrent emergency contraception utilization.

**Primary Outcome:** The **primary outcome** of this study is unintended pregnancy following emergency contraception at both 5 weeks and 6 months post-enrollment.

**Secondary Outcomes:** 1. Long acting reversible contraception (LARC) use at 6 and 12 months following method allocation will be evaluated. 2. Continuation and satisfaction among participants in the LNG-IUS arm.

**Potential Confounders:** There are a number of variables that make act as potential confounders. These variables will be tested for their association with the primary outcome and treatment assignment. Age is strongly associated with fertility. Other potential confounders include: race/ethnicity, socioeconomic status (measured by income or education level), history of sexually transmitted infection or pelvic inflammatory disease, previous or current contraceptive method. Given random assignment, we expect two arms will be balanced in terms of known and unknown confounding variables. However, if any imbalance is noted, we will control for possible confounders in our multivariable statistical analysis.

**Data Management:** Study staff located within the Division of Clinical Research will be responsible for data collection, entry, and management. Off-site staff will enroll participants remotely using the RedCap secure website. All telephone follow up surveys will be conducted by study staff of Washington University in St. Louis, School of Medicine. Data from telephone interviews will be entered using a secure web portal and stored on secure Washington University in St Louis Department of Obstetrics and Gynecology servers. All participants will be assigned a study identification number. This study I.D. will be used on all data forms and for all computer entries. Data entry will be completed using a custom software package (Illume™; DatStat Inc., Seattle, WA). The data manager will be responsible for data processing, validity checks, and communication with the team on data issues.

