#### **Statistical Approach & Data Analysis:**

**Preliminary Analysis:** Descriptive analyses will include comparison of the baseline characteristics of participants in the two treatment arms. Continuous variables will be summarized using means, medians, and standard deviations. Categorical variables will be presented as frequencies. Continuous variables that are normally distributed will be analyzed with Students T-test, and for those that are not normally distributed nonparametric tests will be used. Chi-square and Fisher's exact will be used to analyze ordinal variables.

**Primary Aim:** Observed pregnancies in the LNG-IUS group will be compared to those in the oral group. Because our primary outcome, pregnancy rate (yes/no) is a dichotomous variable, logistic regression will be used.

**Secondary Aim1:** One secondary aim is to evaluate long-acting reversible contraception (LARC) use at 6 and 12months. We hypothesize that women randomized to the LNG-IUS group will be more likely to be using a LARC method. This categorical variable (yes/no use) will be presented as frequency of LARC use in the two groups. Chi-square and logistic regression will be used for analysis.

**Secondary Aim2:** Continuation and satisfaction in LNG-IUS arm will be evaluated. Both continuation and satisfaction will be assessed as dichotomous variables. Continuation and satisfaction (satisfied/ not satisfied) will be presented as frequencies and analyzed with Chi-square and logistic regression.

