**Secondary Aim2:** Long-acting reversible contraceptive (LARC) use (either an IUD or contraceptive implant) at 6 and 12 months will be compared between the two randomization groups and presented as frequencies. Women who become pregnant will be censored at that point, as well as those who stop the method because they desire pregnancy. Use of LARC and satisfaction in the LNG-IUD arm will be assessed as an ordinal variable and models with ordered logistic regression analysis.. We will compare women lost-to-follow up with the baseline sample to assess whether they vary on demographic factors or method type. If we detect non-random loss-to-follow-up, we will consider the impact on the interpretation of our results.

**Right to Withdraw or Removal from Study:** Participants are free to withdraw from this study at any time. The subject must inform the Investigator immediately if they intend to withdraw. To terminate the subject's participation in this study, they must contact PI listed on the informed consent form. They will be asked complete a brief end-of-study telephone interview. Their decision to participate in this study or to withdraw from this study will not influence the availability of their future medical care and will involve no penalty or loss of benefits to which they are otherwise entitled.

Study Principal Investigators, the FDA, or NEIRB (central IRB) can remove the subject from this study without their consent for any reason, including, but not limited to:

- a. Investigator judgment that any condition or circumstance may jeopardize their welfare or the integrity of the study.
- b. Participant fails to follow the instructions of the investigator(s).
- c. Side effects or complications experienced by the participant.
- d. If the study is stopped by the sponsor, Data Safety and Monitoring Board (DSMB), investigators, FDA, or NEIRB prior to completion.

**RISK MANAGEMENT:** All other known risks will be disclosed to the subject via the informed consent process.

Risks of either method of EC are outlined in the package insert and this protocol. There is also a risk of unintended pregnancy. Patients with a positive pregnancy test will be provided with options counseling.

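### Two unreconciled analysis sections for the LNG-IUS-arm aim: one analyses continuation of the device, the other analyses use of any LARC, and the plan does not say which governs

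*Combined protocol and SAP*

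**What the plan says.** The aim is set in the APPROACH section under Secondary Aim 2: to "quantify the contraceptive continuation and satisfaction rates of the participants randomized to LNG-IUS". The next sentence fixes the object and the horizon: "if women have access to the LNG-IUS in this time period, most will continue use for at least 12 months". The hypothesis is "Greater than 70% of women receiving the LNG-IUS as EC will have continued use and satisfaction". Question 4 of the INNOVATION section asks the same thing at 6 and 12 months.

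The Secondary Outcomes paragraph under Evaluation/ Follow-Up lists LARC use as outcome 1 and, separately, "Continuation and satisfaction among participants in the LNG-IUS arm" as outcome 2.

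Two analysis sections follow, one on each side of the sample-size paragraph.

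- Statistical Approach & Data Analysis, Secondary Aim2: "Continuation and satisfaction in LNG-IUS arm will be evaluated", and "Both continuation and satisfaction will be assessed as dichotomous variables". Frequencies, chi-square and logistic regression are named. LARC use is handled separately as Secondary Aim1.
- Data Analysis/Statistical Methods, Secondary Aim2: LARC use, defined as "either an IUD or contraceptive implant", is compared between arms at 6 and 12 months and given as frequencies. Women who become pregnant, or who stop because they want a pregnancy, are censored. Then: "Use of LARC and satisfaction in the LNG-IUD arm will be assessed as an ordinal variable", with ordered logistic regression.

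The Abbreviation Note says that an IUD may be copper or hormonal.

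**The concern.** Continuation of the LNG-IUS and use of any LARC are different quantities, and the aims and the outcome list treat them as different. They diverge for one group: women who give up the LNG-IUS and take an implant or a copper IUD. Such a woman should count as a user in the between-arm LARC comparison, which asks whether offering an IUD as EC leaves more women on highly effective methods. She should not count as a user in an aim about whether women keep the device they were given.

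Under the later section's definitions nothing separates her from a woman who kept the LNG-IUS, and that section has no other within-arm analysis from which continuation could be recovered. At stake is the statement the trial can make about the 70% hypothesis. With two definitions in current text, the choice between them could also be made after the data are seen.

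**Working it through.** The point rests on the text. The plan derives no figure here, since 70% is a hypothesis and not a calculated value. The two sections compare as follows.

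| | Statistical Approach & Data Analysis | Data Analysis/Statistical Methods |
|---|---|---|
| Secondary Aim1 | LARC use, between arms | Women who decline versus women who enroll |
| Secondary Aim2 | Continuation and satisfaction, LNG-IUS arm | LARC use between arms, then LARC use and satisfaction in the LNG-IUS arm |
| Variable type, LNG-IUS arm | Yes/no | Ordinal |
| Method, LNG-IUS arm | Frequencies, chi-square, logistic regression | Ordered logistic regression |
| Continuation mentioned | Yes | No |
| Test or interval against 70% | None | None |

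**Direction.** Let n be the women followed in the LNG-IUS arm, k those still using the LNG-IUS, and s those who switched to another LARC. Let a and b be the numbers satisfied among the k and the s.

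- Continuation is k/n and any-LARC use is (k + s)/n. The difference is s/n, which is never negative. Each 1% who switch adds exactly 1 point.
- The joint proportion is a/n for the LNG-IUS and (a + b)/n for any LARC. The difference is b/n, which lies between 0 and s/n, so each 1% who switch adds at most 1 point.
- Satisfaction alone among current users is a/k against (a + b)/(k + s). It rises if b/s exceeds a/k and falls if b/s is lower. The plan gives neither the denominator nor the wording of the question, so the sign is open.

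**Size (illustration only).** The inputs from Power Analysis and Sample Size are 399 women in the LNG-IUS arm and about 20% loss by 6 months: 399 × 0.8 = 319.2, taken as 319. Loss at 12 months is not given, so 319 may be too many for that time point. True continuation and switching are assumptions; the documents give neither. To exceed 70%, at least 224 of 319 women must be counted (0.70 × 319 = 223.3). Binomial probabilities of observing more than 70% are:

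| True continuation | Counting LNG-IUS only | Plus 2% switching | Plus 5% | Plus 8% | Plus 10% |
|---|---|---|---|---|---|
| 68% | 0.22 | 0.49 (LARC use 70%) | 0.88 (73%) | 0.99 (76%) | about 1.00 (78%) |
| 65% | 0.03 | 0.12 (67%) | 0.49 (70%) | 0.88 (73%) | 0.98 (75%) |

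These rows sit just below the threshold on purpose. If true continuation is already above 70%, or further below it than the switching rate can bridge, the definition changes the number but not which side of 70% the true proportion falls on. The table treats continuation alone; for the joint proportion the shifts are upper limits.

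**The case against.** The strongest reply is that nothing has been replaced. The earlier analysis section is current text and still analyses continuation and satisfaction as yes/no variables, and the aim and the outcome list still carry them. The later section renumbers the aims: its Secondary Aim2 opens with the between-arm LARC comparison, so the sentence about the LNG-IUD arm may be a within-arm LARC model under that aim, or loose wording for use of the LNG-IUS. The censoring sentence just before it speaks of stopping the method, which leans towards method-specific follow-up. The section nowhere says that LARC use is its measure of continuation.

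All of this stands, and it makes the point conditional. A reader might infer that the continuation aim has been dropped, or that switchers will count towards it. The documents do not support that: it follows only if the later section governs and its LARC use is taken as continuation. The parallel wording of the two Aim2 paragraphs makes that reading plausible, and the plan contains nothing to exclude it.

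Three further inferences are tempting and unsupported. One is that satisfaction would be overstated as well; for satisfaction alone the direction is open. Another is that women who stop because of side effects are the ones most likely to be hidden; the plan lists common reactions to the device but says nothing about who switches, or to what. The third is that the trial would report a particular inflated percentage against 70%. For the LNG-IUS arm the later section names a regression model, neither section gives a decision rule, and any such percentage depends on assumed inputs.

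It is also fair to say that this is a single-arm secondary outcome without a power claim, and that contraceptive use is asked about at the follow-up calls, so switchers can probably be separated at analysis. That limits the harm and makes the repair cheap, but it does not settle which definition will be reported.

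**Conclusion.** The concern holds in conditional form. The plan states the LNG-IUS-arm endpoint in two conflicting ways, differing in what is measured (the device or any LARC) and in variable type (yes/no or ordinal), and does not say which applies. If the later section is followed and its LARC use is read as continuation, the reported continuation and joint proportions can only equal or exceed the true ones, by 1 point and at most 1 point respectively for each 1% of followed women who switch. That could alter the conclusion only if the true value lies just below 70%. How likely this is cannot be judged, because the documents give no switching rate. The primary pregnancy comparison is not affected. The point merits correction because the hypothesis carries a stated threshold and the repair is nearly free.

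**What to change.** Merge the two analysis sections into one, with a single numbering of aims, and state:

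1. **Between-arm aim.** Use of any LARC at 6 and 12 months, yes/no, with switchers counted as users.
2. **LNG-IUS-arm aim.** LNG-IUS still in use at 6 and 12 months, yes/no. Switching to another LARC counts as discontinuation. State how an expelled and replaced device is classified. Satisfaction refers to the LNG-IUS, so a woman who has stopped it cannot count as continued and satisfied.
3. **Analysis against the hypothesis.** Report the joint continued-and-satisfied proportion with a 95% confidence interval set against 70%. Drop the ordinal treatment of yes/no LARC use.
4. **Censoring.** Say how the rule for women who become pregnant, or who stop because they want a pregnancy, applies to item 2. At a fixed time point, censoring must mean either leaving a woman out of the denominator or counting her as not continuing; the section should choose one and give the numbers.
5. **Switchers.** Report the number who moved to another LARC on its own line.

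The cost is wording. Evaluation/ Follow-Up already provides for recent and current contraceptive use at the follow-up calls; the sponsor should confirm that the survey records which device is in use. The continuation figure may be slightly less favourable. The interval also sets a stricter standard than a bare percentage: with 319 women, an exact 95% interval lies above 70% only from 240 women upward (240/319 = 75.2%).

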### **Power Analysis and Sample Size**

Power analysis and Sample size calculation was performed with Epi-Info v 6.0.

**Sample Size:** With an alpha ( $\alpha$ ) = 0.05, power of 90%, and assuming unintended pregnancy rates (total 5 weeks through 6 months) of 11% for the oral UPA regimen and 2% for the LNG-IUS, and a 3:1 ratio of LNG-IUS allocation to UPA, we calculate our sample size to be 532 participants (399 LNG-IUS and 133 UPA). This accounts for approximately 20% loss to follow-up rate by 6 months. We chose a 3:1 ratio of LNG-IUS to UPA to allow for a more precise estimate of immediate failure rates of the LNG-IUS group.

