### **Data Analysis/Statistical Methods:**

**Preliminary Analysis:** Descriptive analyses will include comparison of the baseline characteristics of participants in the two treatment arms. Continuous variables will be summarized using means, medians, and standard deviations. Categorical variables will be presented as frequencies. Continuous variables that are normally distributed will be analyzed with Students t-test, and nonparametric tests will be used for those that are not normally distributed. Chi-square and Fisher's exact tests will be used to analyze categorical variables.

**Primary Aim:** Observed pregnancies at 5-6 weeks and at 6 months in the LNG-IUD group will be compared to those in the oral UPA group. The analysis population is enrolled women who complete 5-6-week and 6 month follow-up. "Modified" intent to treat analysis will be used. Pregnancies will be presented as frequencies and chi-square tests will be used for analysis. We expect the two groups to be balanced on important confounding variables such as menstrual cycle day at the time of unprotected intercourse. However, if there are significant imbalances, stratified or multivariable analysis will be performed. Pregnancies at 5-6 weeks and 6 months will be compared by intervention arm with Kaplan-Meier estimates, using dating from last menstrual period time. Logistic regression will be used to control for confounding (if necessary) using the dichotomous outcome of pregnancy (yes/no) at each time point.

**Secondary Aim1:** Descriptive analyses will be used to compare demographic characteristics of participants who screen eligible, but decline to participate and those who enroll in the study. Reasons for declining participation will also be collected and qualitatively evaluated for recurrent themes.

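### The completer-only primary analysis may drop known pregnancies, and the one stated check on loss cannot show pregnancy-related loss; the LNG-IUS failure rate is more exposed than the superiority test

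*Combined protocol and SAP*

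**What the plan says.** Under Data Analysis/Statistical Methods, Primary Aim, the population is defined in one sentence: "The analysis population is enrolled women who complete 5-6-week and 6 month follow-up". The analysis is labelled a modified intent-to-treat analysis, and the modification is not defined. Pregnancies are to be compared by chi-square, with logistic regression for confounding if needed. Kaplan-Meier estimates by arm are also planned, but no censoring rule is given for women who are lost.

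Loss to follow-up is addressed in the same section under Secondary Aim 2, after LARC use and satisfaction: "We will compare women lost-to-follow up with the baseline sample to assess whether they vary on demographic factors or method type". The consequence is: "If we detect non-random loss-to-follow-up, we will consider the impact on the interpretation of our results".

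The sample size allows for substantial loss: "This accounts for approximately 20% loss to follow-up rate by 6 months". No imputation, weighting, bounds, tipping-point or other sensitivity analysis for missing pregnancy outcomes is named anywhere.

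**The concern.** Two features of the plan act together.

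- **The completer rule.** Pregnancy at 5 weeks is itself part of the primary outcome. If completion of both contacts is required, a woman with a confirmed early pregnancy who then misses the 6-month call leaves the analysis, and an observed event goes with her.
- **The loss check.** Baseline demographics and method type do not carry information on whether a woman dropped out because she was pregnant or because the device was removed. Finding no difference therefore does not make completers representative, and finding one leads to no named analysis.

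At stake are the estimated failure rates, above all the LNG-IUS rate, because the 3:1 allocation was chosen to estimate immediate LNG-IUS failure more precisely. Pregnancy is a rare outcome here, so a few events left out or unseen change that rate noticeably.

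**Working it through.** **Inputs** (Power Analysis and Sample Size): alpha 0.05 (two-sided assumed, as sidedness is not stated), power 90%, rates "of 11% for the oral UPA regimen and 2% for the LNG-IUS", 3:1 allocation, 399 LNG-IUS and 133 UPA, about 20% loss.

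**1. The plan's own sample size.** Pooled-variance formula for two proportions, with mean rate (0.11 + 3 × 0.02)/4 = 0.0425:

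n(UPA) = [1.960 √(0.0425 × 0.9575 × 4/3) + 1.282 √(0.11 × 0.89 + 0.02 × 0.98/3)]² / 0.09² = 93.6.

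The continuity correction, n/4 × [1 + √(1 + 2(4/3)/(0.09n))]², gives 107.9, so 108 UPA and 324 LNG-IUS, 432 evaluable. Dividing by 0.80 gives 540, which is 1.5% above the stated 532. The figure reproduces, so the 20% allowance is built into it.

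**2. Expected loss and events**, with equal 20% loss in both arms and the planned rates among completers:

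- Lost: 532 × 0.20 = 106.4 (26.6 UPA, 79.8 LNG-IUS).
- Pregnancies among completers: 0.80 × 133 × 0.11 = 11.7 UPA, and 0.80 × 399 × 0.02 = 6.4 LNG-IUS; total 18.1.
- Ratio: 106.4/18.1 = 5.9. Against all expected pregnancies (14.6 + 8.0 = 22.6) it is 4.7. With 10%, 15% or 25% loss, the completer-based ratio is 2.6, 4.2 or 7.8.

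**3. Tipping points for the superiority test.** In whole numbers the completers are 12/106 UPA v 6/319 LNG-IUS (Fisher p = 0.0002), with 27 and 80 women lost. Add back all lost women and raise the number of pregnancies among lost LNG-IUS women until p exceeds 0.05:

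| Lost UPA women pregnant | Lost LNG-IUS women pregnant at tipping | Table | Fisher p |
|---|---|---|---|
| 0 of 27 | 12 of 80 (15%) | 12/133 v 18/399 | 0.079 |
| 3 of 27 (11%) | 18 of 80 (22.5%) | 15/133 v 24/399 | 0.054 |

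Uncorrected chi-square tips at 12 and 19 of 80. If lost LNG-IUS women conceived at the planned UPA rate (80 × 0.11 = 8.8, so 9), Fisher p is 0.022 with no lost UPA pregnancies (12/133 v 15/399) and 0.004 with three (15/133 v 15/399).

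With fewer UPA pregnancies among completers than expected, the margin narrows. From 11 observed, the tipping points are 9 of 80 (no lost UPA pregnancies) and 16 of 80 (three); from 10, they are 8 and 13 of 80.

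**4. The LNG-IUS failure rate.** Completers: 6/319 = 1.9%. With lost women at the planned 2% (80 × 0.02 = 1.6, so 2): 8/399 = 2.0%. With lost women at 11%: (6 + 9)/399 = 15/399 = 3.8%, double the completer figure.

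**5. What the check can see.** It compares lost women with a sample that contains them. If 20% are lost, a baseline mean for everyone is 0.2 × lost + 0.8 × retained, so the comparison shows only 0.8 of the lost-versus-retained difference. The larger limit is that pregnancy status after loss is not among the variables compared.

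**The case against.** The strongest case on the other side has four parts.

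**The comparison is not fragile at the planned rates.** A reader might infer that a handful of unseen pregnancies would overturn the result. The plan's figures do not support that. Tipping the expected result needs 15% of lost LNG-IUS women pregnant against none of the lost UPA women, when the planned rates are 2% and 11%. The thresholds of 8 or 9 of 80 arise only if UPA pregnancies among completers are also below expectation and no lost UPA woman is pregnant. This objection stands.

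**The six-to-one ratio does not measure bias.** It shows how much is unobserved, rests on a planning allowance, and falls to 4.7 when all expected pregnancies are counted. This also stands; the ratio is context only.

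**The plan is not bare.** Kaplan-Meier estimates can use partial follow-up. The loss check includes method type, so differential loss by arm is examined. The text names no test or threshold and does not bar further analysis, so it would be wrong to read the check as deciding whether anything else may be done. Outcomes can also be recovered: the follow-up surveys ask about interval pregnancies, women who suspect pregnancy are asked to come in, withdrawing women are asked for a closing interview, and the Retention Plan uses alternate contacts. All true, but these steps collect data and do not say how it is analysed. A pregnancy first reported at 12 months by a woman who missed the 6-month call would still fall outside the completer population.

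**Completion may be meant per time point.** Logistic regression is planned at each time point, so the loss of a known 5-week pregnancy is one reading and not an established exclusion. That is fair, but the population sentence joins the two contacts, and the plan should not leave this open.

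**Conclusion.** The concern holds in a limited form. As written, the completer rule can drop an observed primary event, the Kaplan-Meier analysis lacks a censoring rule, and the one stated check on loss cannot show loss related to pregnancy and leads to no named analysis. This is a stated rule that can bias the result, so it goes beyond missing detail.

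The main risk is to the estimates. The LNG-IUS failure rate could be 3.8% where completers show 1.9%, while the superiority test would survive that same scenario. The documents do not support a claim that the trial's conclusion would probably flip.

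These figures assume two-sided alpha, equal 20% loss in each arm, planned rates among completers, and expected counts rounded to whole women. The 11% rate in lost LNG-IUS women is a sensitivity value and not a forecast. The change should be made, and made before outcomes are examined, so that the handling of missing outcomes is not chosen after the fact.

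**What to change.** In the SAP text for the primary aim and for loss to follow-up:

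1. Count every known pregnancy in the randomised arm, at the time point to which it is dated, whatever follow-up is later missed.
2. Include all randomised women in the time-to-event analysis, censored at last contact if no pregnancy is known. State what the modification to intent to treat is, or remove the label.
3. Add a tipping-point table over assumed pregnancy rates in lost women, by arm, covering at least lost UPA women at zero and at 11%. Report the estimated rates as well as the p-values. Censoring alone assumes that loss is unrelated to pregnancy, so this table is still needed.
4. Compare lost with retained women within each arm, as description only and not as a trigger.

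The cost is SAP wording and a short extra analysis, with no new visits, data items or participants. The downside is that the stated result may look slightly less certain.

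### Women may be removed from the study for non-adherence or side effects, no later pregnancy follow-up is provided for, and the primary analysis keeps only women who complete follow-up

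*Combined protocol and SAP*

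**What the plan says.** **Removal.** The Right to Withdraw or Removal from Study paragraph of the combined protocol and SAP allows removal without consent for any reason. Two listed grounds are "Participant fails to follow the instructions of the investigator(s" and "Side effects or complications experienced by the participant". What the woman is removed from is the study, not only the assigned method. The paragraph does not say whether pregnancy is still ascertained afterwards. The one exit contact, a short telephone interview, is described with voluntary withdrawal.

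**Analysis population.** Under Data Analysis/Statistical Methods, Primary Aim: "The analysis population is enrolled women who complete 5-6-week and 6 month follow-up". The analysis is called a modified intent-to-treat analysis, and the modification is not defined.

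**Loss to follow-up.** The plan compares lost women with the baseline sample on demographic factors and method type and, if loss looks non-random, considers this when interpreting the results. It names no imputation or sensitivity analysis.

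**Planning figures.** Power Analysis and Sample Size assumes pregnancy rates "of 11% for the oral UPA regimen and 2% for the LNG-IUS", with "a 3:1 ratio of LNG-IUS allocation to UPA", and adds: "This accounts for approximately 20% loss to follow-up rate by 6 months".

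**The concern.** Read together, the two rules permit exclusion after randomisation on grounds that may be linked to both treatment and outcome. A woman removed before 6 months has no provision for the 6-month call, and without that call she is outside the primary population. Redefining the population later cannot repair this, because the outcome would not have been collected.

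The arms differ in ways that make unequal removal plausible. UPA is a single tablet taken under observation at enrollment. The LNG-IUS involves an insertion, a continuing device and an extra string-check visit. The Risks and Benefits section lists bleeding alterations in 51.9% and amenorrhea in 23.9% of LNG-IUS users.

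If removed women had a higher pregnancy risk than those who stayed, the LNG-IUS failure rate would be understated. The sample-size section gives precision of that arm's immediate failure rate as its reason for unequal allocation, so the rate matters in itself as well as for the test.

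**Working it through.** **1. The plan's sample size.** Inputs from Power Analysis and Sample Size: alpha 0.05 (two-sided assumed, since sidedness is not stated), power 90%, p1 = 0.11 (UPA), p2 = 0.02 (LNG-IUS), k = 3.

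- Pooled rate: (0.11 + 3 × 0.02)/4 = 0.0425.
- n(UPA) = [1.96 √((1 + 1/3) × 0.0425 × 0.9575) + 1.2816 √(0.11 × 0.89 + 0.02 × 0.98/3)]² / 0.09² = 93.6.
- With continuity correction: (93.6/4) × [1 + √(1 + 2 × 4/(3 × 93.6 × 0.09))]² = 107.9, so 108 UPA and 324 LNG-IUS, 432 evaluable.
- Allowing for 20% loss: 432/0.80 = 540.

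The plan says "we calculate our sample size to be 532 participants (399 LNG-IUS and 133 UPA". That is within 1.5% of 540, so the figure reproduces and the sample size is not at fault.

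**2. Effect on the LNG-IUS rate (assumed inputs).** The documents give neither a removal proportion r nor a pregnancy risk q among removed women. I took r = 5-10% and q = 2-11%, running from the planned LNG-IUS rate to the planned UPA rate, and set the completer rate at 2%.

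As-randomised rate = (1 − r) × 2% + r × q

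| | q = 2% | q = 5% | q = 11% |
|---|---|---|---|
| r = 5% | 2.0% | 2.15% | 2.45% |
| r = 10% | 2.0% | 2.3% | 2.9% |

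In counts, r × 399 is about 20 to 40 women. At q = 11% they have 2.2 to 4.4 pregnancies. At q = 2% there is no bias.

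**3. Effect on the superiority test.** With 20% loss, about 0.8 × 133 = 106 UPA and 0.8 × 399 = 319 LNG-IUS women are evaluable. Expected pregnancies are 0.11 × 106 ≈ 12 and 0.02 × 319 ≈ 6. I held the denominators fixed, raised the LNG-IUS count and used the uncorrected chi-square, N(ad − bc)²/(product of the margins):

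- 18 pregnancies: 425 × (12 × 301 − 94 × 18)²/(106 × 319 × 30 × 395) = 3.91, p = 0.048.
- 19 pregnancies: 425 × (12 × 300 − 94 × 19)²/(106 × 319 × 31 × 394) = 3.39, p = 0.066.

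Significance is lost at 19, which is 19 − 6 = 13 unobserved pregnancies, against the 2.2 to 4.4 in step 2.

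**4. Power of an as-randomised comparison.** Using the normal approximation without continuity correction at the same evaluable numbers, power is 92.8% if the LNG-IUS rate is 2.0% and 85.4% if it is 2.9%. A harsher assumption, 15% removed at 20% risk, gives 0.85 × 2% + 0.15 × 20% = 4.7% and power of 61.8%. Nothing in the documents points to values that high.

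**The case against.** The strongest reply is that the clause is permissive. It says who may remove a woman, not that side effects or non-adherence lead to removal, and no section says data collection stops when she is removed. That stands: the gap is the absence of a provision for continued follow-up, not a stated rule ending it.

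Four stronger readings are tempting, and the documents do not support them.

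- *Stopping the device ends follow-up.* The plan points the other way. Continuation is a secondary outcome with a hypothesis of more than 70%. The telephone surveys ask about current contraception and interval pregnancies. Women who stop in order to conceive have their own censoring rule in the LARC analysis. Women who only stop the device are meant to be followed.
- *Removals fall mainly in the LNG-IUS arm.* This is inference. UPA also has listed reactions (headache 18%, abdominal pain 12%, nausea 12%), and the home test and calls apply to both arms. Equal removal proportions under 3:1 allocation would put 75% of removals in the LNG-IUS arm by count without making the proportions differ.
- *The continuation rate is biased upward.* The completer restriction is written under the Primary Aim, and nothing extends it to continuation.
- *The superiority result is at risk.* Step 3 shows otherwise for the range used.

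The 11% upper value is probably high for women removed later. It covers the whole period to 6 months, including failures from the index act, whereas they would be at risk only for the remaining months.

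The Kaplan-Meier estimates do not close the gap. They could use time up to removal, but the stated population still requires both follow-ups, and censoring at removal for a device problem may be informative.

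**Conclusion.** The concern holds as a gap in follow-up and analysis rules. The plan permits removal from the study on grounds that may relate to treatment and outcome, provides for no pregnancy ascertainment afterwards, and restricts the primary analysis to completers. Under assumed removal of 5-10% of the LNG-IUS arm and an assumed risk of 2-11% among those women, the as-randomised LNG-IUS rate is 2.0-2.9%, against 2.0% among completers. The bias is nil if removed women have the same risk as the rest. The likely harm is an understated LNG-IUS failure rate. Reversal of the comparison with UPA is unlikely. Both the direction and the size depend on removal rates and risks that the documents do not give. The change is worth making because the missing outcomes could not be recovered afterwards.

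**What to change.** In Right to Withdraw or Removal from Study, add that non-adherence, side effects, stopping the method or removal by the investigator does not end follow-up for pregnancy and contraceptive use. The 5-week, 6-month and 12-month calls continue unless the woman withdraws consent for contact.

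In Data Analysis/Statistical Methods, Primary Aim, state that these women are analysed in their randomised arm and that removals are reported by arm and reason.

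The cost is protocol wording and slightly more follow-up effort, within calls that the Retention Plan and Study Flow sections already schedule. The sample size does not change. No change to clinical rules on stopping treatment is proposed.
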